Samples for microbiome analysis were collected at baseline (Visit 1), Day 14 (Visit 2), and Day 90 (Visit 4). Before collecting samples, each patient was asked to rinse with plain water prior and rest for 5 minutes. Sample collection was performed by gently wiping the buccal and tongue mucosa separately 10 times with three different cotton swabs. Samples were allowed to air dry at room temperature and individually placed in labeled containers with the patient's unique sequential subject identification number and day of collection. These samples were stored in a secure location at -20°C until utilized for microbiome analyses.

[4] Study Design Table

Protocol Study Design and Schedule of Assessments

Evaluation	Screening (0-2wks to Baseline)	Baseline (Visit 1) Day 0	Visit 2 Day 14 (± 3 d)	Visit 3 Day 45 (± 7 d)	Visit 4 Day 90 (± 7 d)
Informed Consent	x				
Inclusion / Exclusion	x	x			
Demographics	x				
Pregnancy Test		x			x
Medical History / Update	x	x	x		x
Medications / Update	x	x	x		x
Periodontal History	x		x		x
Oral Examination	x	x	x		x
Collect Specimen w Swab		x	x		x
Modified Gingival Index / MGI		x	x		x
Bleeding On Probing / BOP	x				x
Probing depth	x	x			x
Turesky modification Plaque Index		x	x		x
Scaling	x				
Eligibility	x				
X-rays		x			x
Enrollment / Randomization		x			
Dispense oral hygiene kit / Diary		x			
Schedule next appt	x	x	x		
Collect residual oral hygiene kit with Diary and distribute oral hygiene kit with Diary for next phase			x	x	
Collect residual oral hygiene kit / Diary					x

[5] Protocol Synopsis

1. Study Title: The Efficacy and Safety of stabilized chlorine dioxide mouth rinse in Therapy of Peri-implant mucositis
2. Study Design: Single Center, randomized, double blind masking, parallel, two-arm clinical study.
3. Objective: The purpose of this study was to analyze efficacy of stabilized chlorine dioxide as a chemical adjuvant for treatment of peri-implant mucositis in a non-surgical treatment protocol with a 3-month follow-up.
4. Study Treatments: 1) Stabilized chlorine dioxide (associated with periodontal basic therapy); and 2) control (placebo associated with periodontal basic therapy).
5. Number of Patients: A total of 54 patients in one clinical site at Stony Brook were randomized, 27 patients received 1) Stabilized chlorine dioxide (associated with periodontal basic therapy); and 27 patients received 2) control (placebo associated with periodontal basic therapy).

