Each subject was enrolled into the study based upon an initial interview and screening examination certifying the following conditions:

INCLUSION CRITERIA

Inclusion criteria included systemically healthy, partially edentulous patients rehabilitated with functional dental implants and prostheses for at least 1 year, at the Department of Periodontics Stony Brook University. All patients were selected from Stony Brook Dental Clinic and were detected with different peri-implant diagnoses.

Patients included had:

1. diagnosis of peri-implant mucositis;
2. at least at one implant;
3. minimum of 20 natural teeth
4. probing depth (PD) \leq 5mm;
5. BOP (bleeding on probing);
6. No radiographic evidence of bone loss beyond the first two threads of the implant.

EXCLUSION CRITERIA

1. Active Periodontitis or Peri-implantitis, which required definitive treatment.
2. Presence of oral local mechanical factors that could have (in the opinion of the PI) influenced the outcome of the study.
3. Presence of orthodontic appliances, or any removable appliances, that impinged on the tissues being assessed.
4. Presence of soft or hard tissue tumors of the oral cavity.
5. Patients treated with systemic antibiotic therapy or periodontal/mechanical/local delivery therapy within 12 weeks prior to study entry and throughout the study duration.
6. Patients chronically (i.e. two weeks or more) treated with non-steroidal anti-inflammatory drugs (NSAIDs) or any medications known to affect soft tissue condition (excluding treatment of Acetylsalicylic acid \leq 100 mg/day).
7. Patients with uncontrolled diabetes, of any type, and/or patients with HbA1c test value $>7.5\%$ dated 3 months prior to the screening visit.
8. Patients who were receiving radiation therapy to the head and neck area and/or receiving immunosuppressive therapy.
9. The presence of any medical or psychiatric condition or any other condition that, in the opinion of the Investigator, could have affected the successful participation of the patient in the study.
10. Drug and alcohol abuse.
11. Patients who were participants in any other clinical study 30 days prior to the start of the study and throughout the study duration.
12. Subject was pregnant (based on pregnancy result) or lactating.
13. Subject was a smoker or had been a smoker within the past 6 months.
14. Any other condition that may have interfered with the study as judged by the PI.

ASSIGNMENT

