6. Performed a Turesky modification of the Quigley-Hein Plaque Index (PI) grading on all natural teeth and implants in the dentition.
7. Assessed bleeding on probing (BOP) on all natural teeth and implants in the dentition.
8. Verified data capture.
9. X-rays
10. Full mouth Scaling
11. Randomization and dispensation of the Oral Hygiene Kit and Oral Hygiene Diary.
12. The subjects then followed their normal oral-hygiene procedures with the addition of using the study rinse, toothbrush, and toothpaste provided to them.
13. Provided diary for recording use of product rinse or placebo.
14. Provided supplies for 14 days (day 1 to day 14 of the study). Weighed and recorded the weight of test rinse or placebo, as applicable, being provided.
15. Instructed Subject to bring remaining oral rinse or placebo bottle
16. Scheduled following appointments for Visit 2 (2 weeks after base line) and Visit 3 (3 months) and noted in their study instructions and diary. Subjects were to be seen within plus or minus 7 days.

VISIT 2 - INTERIM EXAMINATION - DAY 14

This examination took place within 14 calendar days after Baseline Examination (Visit 1) \pm 3 days. The following procedures were conducted:

1. Reviewed any change in medical and dental history
2. Rinsed mouth with water and collected samples for microbiome analysis by using a cotton swab on the inside of the cheek and tongue mucosa.
3. Evaluated extra- and intra- oral areas for any mucosal irritation or pathology.
4. Performed a Modified Gingival Index (MGI) grading on all natural teeth and implants in the dentition.
5. Performed a Turesky modification of the Quigley-Hein Plaque Index (PI) grading on all natural teeth and implants in the dentition.
6. Weighed and recorded remaining test rinse or placebo as applicable.
7. Checked record for use of test rinse or placebo in the diary.
8. Provided diary for recording use of product rinse or placebo.
9. Provided supplies for 30 days (day 15 to day 45 of the study). Weighed and recorded the weight of test rinse or placebo, as applicable, being provided.
10. Confirmed appointment date scheduled for the Compliance Visit (Visit 3). The subjects were given a reminder call 2 - 3 days prior to their scheduled appointment.

VISIT 3 – COMPLIANCE VISIT – DAY 45

This examination took place within 45 calendar days after Baseline Examination (Visit 1) \pm 7 days. The following procedures were conducted:

1. Weighed and recorded remaining test rinse or placebo as applicable.

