2. Checked record for use of test rinse or placebo in the diary.
3. Provided diary for recording use of product rinse or placebo.
4. Provided supplies for remaining 45 days (day 46 to day 90 of the study). Weighed and recorded the weight of test rinse or placebo, as applicable, being provided.
5. Confirmed appointment date scheduled for the Final Examination Visit (Visit 4). The subjects were given a reminder call 2 - 3 days prior to their scheduled appointment.

VISIT 4 - FINAL EXAMINATION – DAY 90

This examination took place within 90 days following the Baseline Examination (Visit 1) \pm 7 days. The following procedures were conducted:

1. Collected the subject's diary and unused products at check-in. All partially used products were assessed for volume remaining and recorded. Used products were retained until after a monitoring visit, and then returned to the Sponsor.
2. Performed pregnancy testing on females of childbearing age.
3. Rinsed mouth with water and collected samples for microbiome analysis by use of a cotton swab on the inside of the cheek and tongue mucosa.
4. Asked the subject to report any changes in medical or dental health since the last visit.
5. Evaluated extra- and intra- oral areas for any mucosal irritation or pathology.
6. Performed a Modified Gingival Index (MGI) grading on all natural teeth and implants in the dentition.
7. Performed a Turesky modification of the Quigley-Hein Index (PI) grading on all natural teeth and implants in the dentition.
8. Assessed bleeding on probing (BOP) and probing depth on all natural teeth and implants in the dentition.
9. X-rays
10. Weighed and recorded remaining test rinse or placebo as applicable.
11. Checked record for use of test rinse or placebo in the diary.

[10] Study Timeline

Using December 2018 as a calendar starting point, the entire month would provide 20 days for recruiting. As the screening, cleaning and baseline visit can be all on the same day we were considering that subjects could begin Study Visit 1 between January 2019 and December 2019. The final study visits was conducted in March 2020. A final report concluded by December 2020.

[11] Statistical Evaluation

The primary objective of this study was to analyze efficacy of stabilized chlorine dioxide as a chemical adjuvant for treatment of peri-implant mucositis in a non-surgical treatment protocol with a 3-month follow-up.

The primary objective was determined by an examination of the following data:

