- a) Gingival inflammation (MGI)

Secondary analyses were the comparison of data with respect to product effectiveness:

- a) Reduction in bleeding on probing (BOP) and Turesky modification of the Quigley-Hein Plaque Index (PI) grading on all natural teeth in the dentition

The primary statistical analytic framework was the repeated measures analysis of variance on three primary outcomes: probing depth, gingival index, and plaque. The primary hypothesis tested was the treatment by time interaction, i.e., did one treatment work better during the observations of these three outcomes? In other words, not just the total change, but also the rate of that change might differ between treatments. The proposed analysis was based on data that were generally normally distributed and similarly. If not, data transformations or link functions were used.

Outcomes

Raw data were collected from examinations of each tooth with regard to probing depth, gingival index, and plaque. Data were collected over three time periods, recorded into patient files, and transferred to Excel Workbooks, with one Workbook per patient. Each Workbook contained three tabs, one for each visit.

The raw data were combined as two levels of indexes for the three measures. The first outcome was a global score index of probing depth, gingival index, and plaque measurement. The global index was derived from individual tooth scores for each measure divided by the number of teeth measured. The second index derived from the same raw data described the three measures in terms of average scores for implant and non-implant teeth.

For the second analysis, implanted tooth data were separated from normal teeth data within each patient. Implant scores for each patient were averaged for probing depth, gingival index, and plaque scores. If a patient had one implant, each score was identical to the single measurement. With more than one implant, a single implant score for each patient was derived from averaging each of the three measures over the three observation periods. Likewise for each patient, the non-implanted teeth measures were averaged for each of the three times of assessment.

Individual patient data of the averages of the implant and non-implant teeth were calculated for each time period and transferred to a master data sheet.

Data Management and Statistical Analysis

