The patients' data on the three measures were recorded within the Excel Workbooks under three tabs representing the first, second, and third clinical observation periods. So each tab recorded three measures. The first and last tabs recorded probing depth, gingival index, and plaque. The second visit included only gingival index and plaque. Each patient had an individual Excel Workbook. Data were sorted into analysis format through two Excel macros that created a single master data for global scores and a single one for implant and non-implant scores. Data files were saved in comma separated value (csv) format in both wide and long formats for R and SPSS data management, inspection, cleaning, and analyses.

Since many individual variable distributions varied substantially from normal, a gamma log-link function was applied to reduce bias in most statistical tests.

Label Key and Lot #s for Peri-Implant Mucositis Study with Stony Brook University

Rowpar Pharmaceuticals, Inc., released the test material label codes after completion of the clinical study and statistical analysis of the data. The products were labelled as follows:

Study Number: SBU-RPR-Peri-Implant Mucositis-2018

Oral Rinse A: ClōSYS Placebo Oral Rinse, Lot #: 2-80516

Oral Rinse X: ClōSYS® Ultra Sensitive (Unflavored) Oral Rinse, Lot #: 8122A 14-80430

Results

Patients

Fifty-two percent (29/56) of patients in both groups had only one implant. Patients in the control group (Group A) had a total of 47 implants: 11 patients had just one implant, 13 had 2, 2 had 3, and 1 had 4 implants. In the test group (Group X), there were 42 total implants in 26 patients: 18 had 1 implant, 9 had 2, and 2 had 3 implants (see Figure 1). Table 1 gives average values (and standard error of the mean) of Gingivitis Index, Plaque score, and Probing depth at baseline.

Figure 1. Bar chart of numbers of implants per person in control group (Group A) and test group (Group X).

[figure not shown]

Table 1. Patient dental measures at baseline.

		n of patients	n of implants	Modified Gingivitis Index (MGI) (sem)	Plaque score (PS) (sem)	Probing Depth mean (sem)
Control Group (Group A)	implants	27	47	2.06 (0.048)	2.77 (0.115)	3.40 (0.109)

	non-implanted teeth			1.87 (0.039)	2.32 (0.101)	2.72 (0.099)
Test Group (Group X)	implants	26	39	2.82 (0.049)	2.84 (0.057)	2.447 (0.080)
	non-implanted teeth			2.01 (0.028)	2.99 (0.078)	2.65 (0.079)

Global Score Analyses

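### Bleeding on probing is a named secondary outcome, but the described data flow never carries it, and no BOP result appears at implants or at natural teeth

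*Combined protocol and SAP*

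**What the plan says.** All references are to the combined protocol and SAP.

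- **Entry.** Section [8] lists BOP as inclusion item 5, separate from the mucositis diagnosis in item 1. It does not say at which site.
- **Collection.** Section [9], Visit 1, step 7: "Assessed bleeding on probing (BOP) on all natural teeth and implants in the dentition". Visit 4, step 8: "Assessed bleeding on probing (BOP) and probing depth on all natural teeth and implants in the dentition".
- **Outcome.** Section [11] gives MGI as the basis of the primary objective and names as a secondary analysis "Reduction in bleeding on probing (BOP) and Turesky modification of the Quigley-Hein Plaque Index (PI) grading on all natural teeth in the dentition".
- **Raw data.** Section [11], Outcomes: "Raw data were collected from examinations of each tooth with regard to probing depth, gingival index, and plaque".
- **Analysis files.** Data Management and Statistical Analysis: "The first and last tabs recorded probing depth, gingival index, and plaque". For the middle visit: "The second visit included only gingival index and plaque".
- **Derived scores.** The global index and the implant/non-implant index are each built from the same three measures.

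**The concern.** A secondary outcome should be traceable from the examination to a result. BOP is collected at both kinds of site and promised in section [11], and then it disappears. The files sent to R and SPSS are not described as containing it, and neither the results nor the conclusions mention it.

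The site wording adds to this. The trial treats mucositis at implants, but the sentence that promises BOP names natural teeth and not implants. If it applies to BOP, the planned analysis would leave out the treated sites even if the data were entered.

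At stake is a separately collected sign that could support or challenge the claim in the Conclusions of a preferential benefit at implant sites. Readers also cannot tell whether BOP was analysed and left out of the report, or never analysed.

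**Working it through.** The plan states no figure for BOP and no sample-size inputs, so there is nothing of its own to reproduce. The main check is a trace; the arithmetic concerns weight and precision.

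**1. Trace**

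| Stage | Where | BOP present? |
|---|---|---|
| Eligibility | Section [8], item 5 | Yes, site not named |
| Examination | Section [9], Visits 1 and 4 | Yes, teeth and implants |
| Outcome list | Section [11], secondary a) | Yes, natural teeth named |
| Repeated-measures framework | Section [11] | No |
| Raw data | Section [11], Outcomes | No |
| Workbook tabs | Data Management | No, at any visit |
| Global and implant/non-implant indices | Section [11] | No |
| Tables 1 to 7, figure captions, conclusions | Results onward | No |

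The figures themselves are not shown in the text available, but no caption names BOP.

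**2. Weight of implants in a whole-mouth score**

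Inputs: at least 20 natural teeth (section [8]); implant counts from Results, Patients, and Table 1. Share = m / (m + 20), where m is mean implants per patient and each tooth or implant counts equally.

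- Control: 11×1 + 13×2 + 2×3 + 1×4 = 47 implants in 27 patients; m = 1.74; share = 1.74/21.74 = 8.0%.
- Test, listed breakdown: 18×1 + 9×2 + 2×3 = 42 implants in 29 patients; m = 1.45; share = 1.45/21.45 = 6.8%.
- Test, 42 implants in the stated 26 patients: m = 1.62; share = 7.5%.
- Test, Table 1: 39 implants in 26 patients; m = 1.50; share = 7.0%.

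More than 20 teeth would lower each share.

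**3. Precision of a comparison by arm**

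Assumed common proportion p of 0.3 to 0.5; patients 27 v 26 (Table 1). SE = √[p(1−p)(1/27 + 1/26)].

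- p = 0.3: SE = 0.126; half-width 1.96 × SE = 0.25.
- p = 0.5: SE = 0.137; half-width = 0.27.
- True difference needed for 80% power, about 2.8 × SE: 0.35 and 0.38.

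**4. Why an all-implants-clear endpoint needs care**

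Patients with two or more implants: control 13 + 2 + 1 = 16 of 27; test 9 + 2 = 11 of 29 on the listed breakdown. Assume no treatment effect and that each implant stops bleeding independently with probability 0.5:

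- Control: (11×0.5 + 13×0.25 + 2×0.125 + 1×0.0625)/27 = 9.0625/27 = 33.6%.
- Test: (18×0.5 + 9×0.25 + 2×0.125)/29 = 11.5/29 = 39.7%.

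The test arm gains about 6 points from implant count alone. The gap falls to zero if implants within a patient always agree. Each patient's share of bleeding implants has the same expected value whatever the implant count, so it avoids this artefact.

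**5. Baseline time point**

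The schedule row "Bleeding On Probing / BOP" appears to mark Screening and Visit 4 only. Section [9] has BOP in the screening examination and again at Visit 1, and synopsis item 7 places it in the baseline examination. The two visits may fall on the same day, but need not.

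**The case against.** **The phrase about natural teeth may qualify plaque alone.** It directly follows the plaque grading. Plaque carries the same phrase and was still analysed at implants (Table 7), so the phrase did not exclude implants in practice. This stands: the wording is ambiguous and cannot carry the point. But on the narrower reading BOP has no stated site set, and it is still missing from the files.

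**MGI already covers inflammation at implants.** It is the primary measure, is graded at implants and is analysed there (Table 6). Section [1] defines mucositis by mucosal inflammation without bone loss and does not mention bleeding. So BOP cannot be called the definitive answer to the trial's question. It remains a promised, separately collected outcome, and it would be informative because implant MGI differed widely at baseline: 2.06 control v 2.82 test (Table 1).

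**Stronger readings that a reader might infer, and that fail:**

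- *That bleeding is evaluated at healthy teeth and discarded at implants.* No BOP result appears at either kind of site. The teeth were not shown to be healthy either: their baseline MGI was 1.87 and 2.01.
- *That BOP at implants cannot be analysed.* The procedures say it was assessed, so source records may allow it. No visit form is in the documents, so this is unconfirmed.
- *That the trial is large enough to show any large effect.* A half-width of 25 to 27 points is not power; about 35 to 38 points would be needed for 80%.

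**Conclusion.** The point holds as a gap in data flow and reporting: a named secondary outcome has no described data path and no result at any site. This follows from the text and needs no assumption. The natural-teeth wording is a secondary weakness that depends on how the sentence is read.

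A whole-mouth score would not remedy the implant question, since implants would make up only about 7 to 8% of it. That figure assumes equal weight per tooth or implant and the minimum of 20 teeth.

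An implant-level comparison would be imprecise: about ±25 to 27 points for a difference in proportions, assuming proportions of 30 to 50% and 27 v 26 patients. The denominators are themselves unsettled: 27 v 26 in Table 1, 56 in the Patients text and 57 in Table 3. The documents do not show that the MGI or plaque results are wrong for want of BOP, only that BOP has not been brought to bear on them.

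**What to change.** 1. Retrieve BOP from source records and add it to the first- and last-visit data.
2. State the site set as implants and natural teeth, reported separately.
3. Take as the main measure each patient's share of bleeding implants (or implant sites) at Day 90. Compare arms with a 95% CI, adjusted for baseline BOP.
4. Show any proportion of patients with no implant bleeding only with account taken of implant count, for example stratified by one v two or more.
5. Reconcile the BOP time points in the schedule, section [9] and the synopsis, and say which reading is baseline. Reconcile the patient denominators (27 v 26, 56, 57) before fitting anything.
6. Label the implant-level definition post hoc. Label codes were released after the statistical analysis, so it can no longer be presented as prespecified.
7. If the records cannot be retrieved, state that the BOP secondary outcome was not analysed, and limit the conclusions to plaque and gingival index.

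The cost is record retrieval, data entry for two visits and a short analysis. The downside is a wide interval, which should be presented as an estimate and not as a test that could settle the question.

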Once a subject had been screened and qualified for study participation, that subject was enrolled and assigned the next available randomization number. The study randomization table was generated by a third-party statistician. This procedure was used to keep the Study Statistician blinded to subject treatments prior to database lock.

WITHDRAWAL

Subjects enrolled in the study were able to elect to withdraw at any time for any reason. Additionally, subjects were able to have been withdrawn from the study at the request of the Principal Investigator for the following reasons:

1. An adverse event required discontinuation of the study rinse in the judgment of the Principal Investigator or designee
2. Subject refused or failed to comply with the study protocol

3. There was a protocol violation(s) or deviation(s) that compromised the use of the subject's data

All patients withdrawn from the study by request or by the Principal Investigator were to be seen, if they consented, for a close-out evaluation. The reason for withdrawal would be recorded by the Principal Investigator or designee on the End of Study form. Patients who experienced complications and discontinued the study on their own were to be scheduled, if they consented, for an immediate follow-up/close-out examination to determine whether an adverse event was present, and if so, the causation of the adverse event was to be recorded. If treatment was needed for any adverse event causing withdrawal, the subject would be monitored until there was a return to normal conditions. (Every effort would be made to follow up with subjects who withdrew from the study.)

Test Product: ClōSYS® Ultra Sensitive Rinse

Placebo: Oral rinse comprising same ingredients as in test product except for stabilized chlorine dioxide.

Materials:

Sponsor shipped prelabelled 'Oral Rinse A' and 'Oral Rinse X' products to the Test Site. Both products were in 16 oz. size bottle and identical in appearance.

Each subject received the following supplies at Baseline (Visit 1) i.e. supplies for 0-14 days:

- a. 1 bottle (16oz) of either Oral Rinse A or Oral Rinse X))
- b. 35 measuring cups
- c. 1 tube of Crest Cavity Protection Toothpaste, Regular (8.2oz) and
- d. 1 ClōSYS toothbrush

Each subject received the following supplies at Visit 2 i.e. supplies for 15-45 days:

- a. 2 bottles (16oz) of either Oral Rinse A or Oral Rinse X)
- b. 70 measuring cups
- c. 2 tube of Crest Cavity Protection Toothpaste, Regular (8.2oz) and

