From raw data of individual teeth, each patient received a global index of periodontal disease, gingival index, and plaque for each visit. The global index for each of these measurements was found by dividing the sums of patient probing depth, gingival index, and plaque findings collected for each tooth by the number of teeth assessed. Over the three assessment periods, global scores of probing depth, gingival index, and plaque were collected for the first and last visits with probing depth scores not collected during the second visit. These outcomes are measured as individual slopes of responses across the three observation visits. The slope represents the rate of change.

The overall view of the response of each measure to the treatment group is summarized in the following general linear model Table 2. Table 3 shows the cell statistics for the slopes of each condition and outcomes reported in Table 2.

Table 2. Master table of variance components attributable to treatment on individual rates of change on the three measures: probing depth, gingival index, and plaque.

Source	Variable	Type III SS	df	MS	F	Sig.
Group	Slope of probing depth, time 1 to 3	0.125	1	0.125	1.191	0.28
	Slope of gingivitis index, time 1 to 3	0.485	1	0.485	11.748	0.001
	Slope of plaque score, time 1 to 3	4.019	1	4.019	69.751	0.000
Error	Slope of probing depth, time 1 to 3	5.75	55	0.105		
	Slope of gingivitis index, time 1 to 3	2.27	55	0.041		
	Slope of plaque score, time 1 to 3	3.169	55	0.058		
Total	Slope of probing depth, time 1 to 3	6.519	57			

Slope of gingivitis index, time 1 to 3	6.135	57
Slope of plaque score, time 1 to 3	18.861	57
Corrected Total	Slope of probing depth, time 1 to 3	5.875
	Slope of gingivitis index, time 1 to 3	2.755
	Slope of plaque score, time 1 to 3	7.187
	R Squared = .021 (Adjusted R Squared = .003)	
	R Squared = .176 (Adjusted R Squared = .161)	
	R Squared = .559 (Adjusted R Squared = .551)	

Table 3. Details of cell statistics for analysis described in Table 2.

Descriptive Statistics					
	N	Minimum	Maximum	Mean	Std. Deviation
Probing depth at time 1	57	2.04	4.63	2.71614	0.432843
Probing depth at time 3	57	0	4.42	2.50351	0.804056
Gingivitis index at time 1	57	1.41	2.23	1.97158	0.172065
Gingivitis index at time 2	57	0	2	1.71754	0.364095
Gingivitis index at time 3	57	0	1.92	1.48456	0.451688
Plaque score at time 1	57	1.47	3.54	2.67895	0.555475
Plaque score at time 2	57	0	3.11	2.19614	0.596444
Plaque score at time 3	57	0	2.92	1.77386	0.618124

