Slope of probing depth, time 1 to 3	57	-1.47	0.015	-0.10632	0.323886
Slope of gingivitis index, time 1 to 3	57	-0.99	-0.03	-0.24351	0.221807
Slope of plaque score, time 1 to 3	57	-1.53	-0.045	-0.45254	0.358255
Valid N (listwise)	57				

Global Probing Depths (GPD)

Global probing depth (GPD) collected at the first visit did not differ significantly between groups; control group's (Group A) initial GPD was 2.76 (SEM = 0.092) interval, and 2.68 (0.071) for test group (Group X), a non-significant statistical difference ($p = 0.48$).

Neither did the GPD score differ between final visits of control group (Group A) (GPD = 2.64 (0.130) and test group (Group X) (GPDI = 2.37, (0.166), $t = 1.27$, $df = 55$, $p = 0.28$. Nonetheless, the GPD decreased significantly for control group (Group A), ($p = 0.028$; for X, $p < 0.001$) for both groups, but the group decreases were not significantly different from each other. Both mouthwashes reduced probing depth similarly.

The key signal of treatment effectiveness is a statistically significant treatment-by-time interaction, where improvement over time is greater for one treatment than another. Nearly parallel lines in Figure 2 and statistical testing indicated no appreciable and significant treatment-by-time interaction for GPD (See Figure 2, Figure 3).

Figure 2. Interaction plot showing that group assignment did not interact with time for probing depth.

[figure not shown]

Figure 3. Boxplots of probing depth results from treatment by control group (Group A) and test group (Group X). Probing depth was not affected differentially by the mouthwash treatments. Both conditions reduced probing depth slightly but not statistically significant.

Global Plaque Score

Control group (Group A) and test group (Group X) differed significantly in global plaque score (GPS) at initial assessment, requiring an additional analysis of covariance to confirm that a significant time by treatment interaction was not an artifact from the initial difference in GPS (See interaction plot, Figure 4, detailed in Figure 5). The test group's (Group X) initial average GPS was 3.00 (SEM = 0.071) versus 2.35 (0.097) for the control group (Group A), a significant difference ($t = -5.45$, $df = 50$, $p < 0.001$). At assessment 3, the last observation, the test group's (Group X) GPS (1.57, SEM = 0.110) was significantly lower than that for the control group (Group A); GPS = 1.98 (0.110), $t = 2.633$, $df = 55$, $p = 0.011$.

[figure not shown]

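### Section [11] names repeated-measures ANOVA with no rule for missed visits; a mixed model on all observed MGI and plaque scores would avoid complete-case loss, for a modest gain.

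*Combined protocol and SAP*

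**What the plan says.** Section [11], Statistical Evaluation, sets the method: "The primary statistical analytic framework was the repeated measures analysis of variance on three primary outcomes", namely probing depth, gingival index and plaque. It adds: "The primary hypothesis tested was the treatment by time interaction". Neither that section nor the data-management text after it says what happens when a patient misses a visit. Under Data Management and Statistical Analysis, "The second visit included only gingival index and plaque", so probing depth has no Day 14 value. The same text says that "a gamma log-link function was applied to reduce bias in most statistical tests", and that files were kept in wide and long layouts for R and SPSS.

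The protocol foresees loss. Under Withdrawal, patients who leave "were to be seen, if they consented, for a close-out evaluation". It does not say that MGI or plaque is scored at that visit.

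Patient numbers differ from place to place. The synopsis says "A total of 54 patients in one clinical site at Stony Brook were randomized". The Results text gives a total of 56, Table 1 has 27 control and 26 test (53), and Table 3 has 57 on every row, including the row "Gingivitis index at time 2".

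**The concern.** Repeated-measures ANOVA fitted as a classical general linear model keeps only patients with a score at every visit entered. A patient seen at Day 14 but not at Day 90 is removed altogether, and the Day 14 score goes unused. The resulting comparison is unbiased only if loss is unrelated to the scores. A likelihood-based mixed model uses each observed score and remains valid when loss depends on scores already seen.

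The plan leaves this open, and the reported tables suggest two different treatments of the same patients: a smaller set in Tables 4-7, and a full set in Tables 2-3 that appears to contain zeros where visits were missed. Correcting the zeros without changing the method would move the global analysis onto the smaller set.

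**Working it through.** **1. Patients behind each table, from the error df.**
- Table 2: 57 - 2 = 55, as printed.
- Tables 5-7: with one row per patient and site type (implant, non-implant) and 4 cells, 53 × 2 - 4 = 102, as printed. 56 patients would give 108 and 57 would give 110.
- Table 4: 53 × 2 × 2 - 8 = 204, as printed.
- 53 = 27 + 26, the arm sizes in Table 1.

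**2. Arm sizes in the set of 57.** Baseline global plaque is 2.35 (control) and 3.00 (test); the pooled mean in Table 3 is 2.67895. Control n = 57 × (3.00 - 2.67895)/(3.00 - 2.35) = 28.2, or 27.7 to 28.6 allowing for rounding. So about 28 control and 29 test. Check against Table 2: the slope difference is √(4.019/(28 × 29/57)) = 0.531, which gives plaque changes of -0.365 and -1.427. The Results state 0.365 (in size) and -1.43.

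**3. Evidence of zeros for missed visits.** Table 3 has a minimum of 0 for probing depth at time 3. A whole-mouth mean probing depth of 0 is not a credible measurement. The lowest slopes (-1.47, -0.99, -1.53) equal (0 - baseline)/2 for baselines of 2.94, 1.98 and 3.06, all within the Table 3 ranges.

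**4. How many zeros.** With k zeros among n values, the rest have sum of squares SS = (n - 1)SD² + n·mean² - (n·mean)²/(n - k), which cannot be negative.

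| Score | n | k | SS left | SD of the rest |
|---|---|---|---|---|
| Day 90 probing depth, control | 28 | 1 | 5.55 | 0.46 (baseline 0.49) |
| | | 2 | -2.24 | impossible |
| Day 90 probing depth, test | 29 | 3 | 3.58 | 0.38 (baseline 0.38) |
| | | 4 | -3.69 | impossible |
| Day 14 MGI, pooled | 57 | 2 | 1.31 | 0.156 |
| | | 3 | -1.92 | impossible |
| Day 90 MGI, pooled | 57 | 4 | 1.94 | 0.193 (baseline 0.172) |
| | | 5 | -0.65 | impossible |

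These are upper bounds. For Day 90 MGI, k = 3 (SD 0.29) and k = 2 (SD 0.36) are also possible. One control and three test zeros fit best, because the remaining spread then matches baseline.

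**5. What a recode would do.** With four zeros at Day 90, 57 - 4 = 53. With at most two at Day 14, at least 4 - 2 = 2 patients would have a Day 14 MGI and no Day 90 MGI, and complete-case ANOVA would discard those scores. This holds only if there are exactly four zeros at Day 90 and all are missed visits.

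**6. Size.** Loss would be 3/29 = 10.3% (test) and 1/28 = 3.6% (control), Fisher p = 0.61. The standard error ratio is √[(1/27 + 1/26)/(1/28 + 1/29)] = 1.037. That bounds the gain, because a patient with only Day 14 adds less than a complete one.

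**The case against.** The strongest reply is that the plan contains no complete-case rule. A gamma log-link model on long-format data need not delete anyone, and Tables 2-3 delete nobody. This stands: a reader might infer that the plan restricts the analysis to patients with every visit, and the text does not say so. The restriction belongs to the classical form of the method. Tables 4-7, with Type III sums of squares and normal-theory F tests, look like that form.

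Nor is the set of 53 uniform. The implant section reports a plaque change with df 55 (57 patients) and a baseline probing-depth test with df 52 (54 patients), and the global MGI covariance analysis has df 51 (54 patients if it contains arm and baseline). The repeated-measures result for global MGI, F = 8.141 with p = 0.0046, does not fit 102 denominator df, which would give p = 0.0052.

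Missed visits are also not the documented cause of the 53. The 27/26 split already stands in Table 1, a baseline table, and the control implant listing has only 27 patients (11 + 13 + 2 + 1), so the back-calculated 28th is absent from it. On the test side the listing has 18 + 9 + 2 = 29 patients with 42 implants against 26 and 39 in Table 1. Three patients and three implants are gone, with no reason given.

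A reader might also infer that Table 2 ignores Day 14 because of deletion. It does not: the mean slopes equal (time 3 - time 1)/2, for example (1.48456 - 1.97158)/2 = -0.24351 for MGI, so the middle visit has no weight for any patient.

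Finally, the apparent zeros matter more than the choice of model. Removing them as counted above moves the Day 90 MGI difference from about 0.25 to about 0.15 and the plaque difference from 0.41 to about 0.30. That stands as a separate and larger point. It does not remove this one, because recoding alone leaves a method that needs complete rows.

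**Conclusion.** The point holds in a limited form. Section [11] names a method that, as classically fitted, needs complete rows, and gives no rule for missed visits in a trial that expects withdrawals. Tables 4-7 fit 53 patients and Tables 2-3 use 57. If the zeros are missed visits, correcting them under the planned ANOVA would leave about 53 and probably lose some Day 14 MGI and plaque scores. The zero counts, the arm split of 28 and 29, and the reason for the 53 come from summary statistics and need patient-level confirmation.

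Three stronger readings are not supported:
- **Differential dropout.** Three against one is too few to show it.
- **Demonstrated bias towards the test rinse.** If those lost would have scored 0.2 to 0.5 MGI points worse (an assumption in size and direction), the shift is (0.103 - 0.036) × 0.2 to 0.5, about 0.01 to 0.03 points.
- **Unused close-out scores.** The documents do not show that any index was recorded at close-out.

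The argument about Day 14 does not apply to probing depth. What remains is a modest improvement: a standard error at most 3.6% smaller (1 - 1/1.037), plus validity when loss depends on observed scores.

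**What to change.** In section [11]:
- **MGI and plaque.** Make the primary analysis a mixed model for repeated measures, with Day 14 and Day 90 scores as responses and arm, visit, arm-by-visit, baseline and baseline-by-visit as fixed effects. Use an unstructured covariance and REML with small-sample df. Include every randomised patient with any post-baseline score, and report the Day 90 arm contrast. The baseline term also adjusts for the MGI difference at entry (2.03 test, 1.91 control).
- **Probing depth.** Use ANCOVA on Day 90 adjusted for baseline.
- **Missing data.** State that an unobserved visit is missing, not zero. Check each zero against the patient workbooks. Use close-out scores only if the indices were recorded then, with a rule for assigning them to a visit.
- **Reporting.** Give N by arm and visit for every table, and reconcile 53, 54, 56 and 57, and the 26 against 29 test patients.
- **Sensitivity.** Keep the complete-case ANOVA.

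The cost is SAP wording, a check of the patient workbooks, and a re-run in R or SPSS from the existing long-format files. No new data are needed.
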